- e Pregnancy test can be performed at home for participants during the FUP or if date of test does not match with FUP visit and the site must record this in the source document. Test should be performed at the end of isatuximab treatment (ie, Week 1 of site visit FUP or E/D visit [± 7 days]), and 5 months (± 7 days) after the last dose of IMP.
- f Post-treatment tests are only applicable for HBV, CMV, and EBV, and only has to be performed at Site Visit FUP Week 9 if baseline result is positive or as clinically indicated. In case HBV vaccination will be started before first study treatment administration, anti-HBs should be monitored at approximately 1, 2, and 3 months after end of vaccination (± 7 days, or at the next blood sampling). For participants with positive anti-HBc and negative HBsAg and undetectable HBV deoxyribonucleic acid (DNA) at study entry (past resolved infection, resolving acute infection, or receiving antiviral treatment with controlled infection), close monitoring of viral reactivation (greater than 1log10 IU/mL increase in HBV DNA or reappearance of HBsAg or detection of HBV DNA in patients with resolved infection) throughout and following the end of study

treatment should be proposed (alanine aminotransferase [ALT], aspartate aminotransferase [AST], and HBV DNA at Site Visit FUP Week 9 and Week 25, or until initiation of further desensitization therapy/transplant surgery). In case of viral reactivation during study treatment (greater than 1log10 IU/mL increase in HBV DNA or reappearance of HBsAg or detection of HBV DNA in participants with resolved infection), close monitoring of ALT and AST approximately every month (may coincide with the next scheduled blood sampling \pm 7 days), up to study treatment discontinuation. HBV DNA to be done as per Investigator's and/or specialist advice.

- g Only if screening result is positive and not tested during site visit FUP.
- h Assessment not required to be repeated prior to Cycle 1 Day 1, if screening assessments were performed within 7 days prior to the first IMP infusion and met the entry criteria. Window for assessment is within 1 working day prior to IMP infusion.

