- i Blood type (if not already done) and phenotype (according to the site protocol). Recommended phenotype includes Rh system (C/c and E/e), Kell system (K/k); Duffyn system (Fya/Fyb); Kidd system (Jka/Jkb); MNS system (M/N, S/s), and indirect antiglobulin test (IAT; indirect Coombs test). Blood type card will be kept by the participant with the study card. Blood type and blood product transfusions are to be recorded in the electronic case report form. The blood bank needs to be informed that the participant is receiving a treatment with an anti-CD38 and a potential interference with the Coombs test is possible (see [Section 10.10](#)). IAT (indirect Coombs test) to be repeated at C2D1 (if not performed at this visit, it can be done at the next blood sampling); if post-treatment (ie, C2D1) IAT (indirect Coombs test) is positive, subsequent tests to be performed at site Visit FUP Weeks 1, 13, and 25, and E/D if discontinued during Site Visit FUP.
- j Blood sample must be collected prior to IMP administration. Window for assessment is within 1 working day prior to IMP infusion.
- k Blood draw time points that do not coincide with site visits may be collected at the local facility or at the participant's home by a health care professional (depending upon local arrangements and preference of the Investigator), provided that samples are collected with designated tubes and per laboratory manual. Blood drawn should be performed prior to dialysis (if dialysis is performed on the same day).
- l Only if site visit FUP sample (ie, Week 17) not collected.
- m Include any desensitization therapy. For participants who proceed to transplantation after E/D, or completion of treatment and/or site visit FUP, also collect immunosuppression regimen.
- n Collect the following information: Start and end date(s) when listed as active candidate on the waitlist for kidney transplant, waitlist ID and transplant center code (if applicable, and if local regulation allows and in line with the most recent participant signed informed consent form), virtual or donor-specific cross matching results, and dates of all transplant offers (if any, indicate whether offers were accepted and reasons of rejecting offers).

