6.5 CONCOMITANT THERAPY

Any medication or vaccine (including over-the-counter or prescription medicines, vitamins, and/or herbal supplements) that the participant is receiving at the time of enrollment or receives during the study must be recorded along with:

- Reason for use
- Dates of administration including start and end dates
- Dosage information including dose and frequency

Prohibited concomitant medications:

Prohibited concomitant medications (until end of Site Visit FUP, or E/D, or participant undergoes transplantation) are described below:

- Concurrent treatment with any desensitization procedure or anti-neoplasm therapy not specified in the protocol, including chemotherapy, immunotherapy, hormonal therapy, targeted therapy, biological therapy, other investigational drug, or curative radiotherapy.
- Concomitant treatment with immunosuppression medications are prohibited, except for:
 - use in premedication defined in the study protocol,

- treatment of any life-threatening emergency,
- low dose corticosteroids (eg, up to 10 mg prednisone/day or equivalent) as needed for Investigator's judgment, and
- a brief course (≤ 7 days) of systemic corticosteroid for prophylaxis (eg, contrast dye allergy) or for the treatment of non-autoimmune conditions (eg, delayed-type hypersensitivity reactions cause by contact allergen).
- Investigational therapy (other than protocol-mandated study intervention) is prohibited within 28 days prior to initiation of IMP, during treatment period, and during site visit FUP.
- Live vaccines should be avoided. However, given the increased risk of infection, routine vaccinations are recommended for the participants and their contacts. Prophylactic vaccination is recommended for influenza A and B virus, pneumococci, and haemophilus influenza.
- Phase 1 only: Prophylactic use of hematopoietic growth factors (eg, G-CSF, granulocyte macrophage-colony stimulating factor [GM-CSF]) during the first cycle observation period. Curative treatment and prophylactic use of erythropoietin is allowed.

Other concomitant medication may be considered on a case-by-case basis by the Investigator in consultation with the Medical Monitor if required.

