1.2.1 Estimands

Primary estimand defined for the main efficacy endpoint is summarized in below [Table 2](#).

Table 2 - Summary of primary estimand for main efficacy endpoint

Endpoint Category (estimand)	Estimands			
	Endpoint	Population	Intercurrent event(s) handling strategy	Population-level summary (Analysis and missing data handling)
Primary efficacy objective: Phase 2: To evaluate the efficacy of isatuximab in desensitization of patients awaiting kidney transplantation				
Primary efficacy endpoint (Estimand 1)	Response rate	Efficacy-evaluable	Interruption/discontinuation of study intervention: Response rate will be analyzed regardless of intervention discontinuation (treatment policy)	Response rate, defined as proportion of participants meeting at least one of the predefined desensitization efficacy criteria, from baseline up to 26 weeks after treatment period and two-sided 95% confidence intervals using the Clopper-Pearson method (1)

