3 ANALYSIS POPULATIONS

The following populations for analyses are defined:

Table 3 - Populations for analyses

Population	Description
Screened	All participants who sign the informed consent form (ICF).
Enrolled	Includes all participants from screened population who plan to continue in the treatment phase upon completion of screening, regardless of whether the study intervention (isatuximab) was received or not.
All treated	Includes all participants who receive at least 1 dose of isatuximab-. This population is the primary population for the analyses of safety parameters, unless otherwise noted. All analyses using this population will be based on the dose level actually received.
Safety-evaluable (Phase 1)	Includes all participants enrolled in Phase 1 who receive $\geq 90\%$ planned cumulative doses of isatuximab within Cycle 1 (unless IMP is discontinued due to pre-defined unacceptable toxicity).
Efficacy-evaluable	Includes All Treated population who fulfill the study eligibility criteria, with an evaluable baseline and at least 1 evaluable postbaseline efficacy assessment and receive $\geq 75\%$ of planned cumulative doses. This is the primary population for efficacy analyses.
PK	Includes All Treated population with at least 1 available concentration result post-treatment (whichever the cycle and even if dosing is incomplete) with adequate documentation of date and time of dosing and date and time of sampling.
ADA	Includes All Treated population with at least 1 available ADA result (negative, positive, or inconclusive) post-treatment (whichever the cycle and even if dosing is incomplete).

Participants exposed to isatuximab before or without being enrolled will not be considered enrolled and will not be included in any analysis population. The safety experience of these participants will be reported separately.

Enrolled participants for whom it is unclear whether they took isatuximab will be considered as treated and will be included in the safety population.

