4.3 PRIMARY ENDPOINT(S) ANALYSIS

4.3.1 Definition of endpoint(s)

The primary endpoint in the Phase 1 portion of the study will focus on safety, ie, AEs/SAEs and laboratory abnormalities. Analysis details of these safety parameters are presented in [Section 4.7.2](#) and [Section 4.7.3.1](#).

In the Phase 2 portion of the study, the primary efficacy endpoint will be RR, to be defined as the proportion of participants meeting at least one of the predefined desensitization efficacy criteria, from baseline up to 26 weeks after treatment period, measured by SAB assay per central laboratory assessment as follows:

- Reduction in cPRA resulting in at least 100% increase of likelihood of finding a compatible donor for target cPRA
- Reduction in antibody titer ($\geq 75\%$ reduction from baseline) to achieve target cPRA
- Elimination of ≥ 1 anti-HLA-antibody (ie, MFI reduced to < 2000) as measured by a SAB assay, for antibodies with baseline MFI ≥ 3000

RR criterion 1: target cPRA

The target cPRA, defined as the reduction of cPRA required to achieve at least 100% increase of likelihood of compatible donor (LCD), is calculated according to the following equation:

$$LCD = 1 \text{ in } \frac{1}{1 - cPRA}$$

Participants with baseline cPRA 100.00% will be assigned with cPRA 99.99% for computational purpose. In addition, cPRA values will be rounded to 2 decimal places prior to LCD calculation ($\geq xx.xx5$ =round up, $< xx.xx5$ =round down).

RR criterion 2: antibody titer

Antibody titer is defined as the last dilution of serum at which positive results is obtained (eg, MFI ≥ 2000). To potentially meet the second RR criterion, serial dilution of the serum collected at baseline is performed until the target cPRA is achieved. If subsequent post-treatment serum is diluted at $\geq 75\%$ reduction from the baseline dilution that achieved target cPRA, and again meet target cPRA anytime within the 26-week post-treatment period, participant will have met RR criterion 2.

RR criterion 3: anti-HLA-antibody

An anti-HLA-antibody is considered to be eliminated if its MFI is reduced to < 2000 at post-treatment. Only antibodies with baseline MFI ≥ 3000 will be included for assessment under this criterion.

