4.3.2 Main analytical approach

The primary efficacy analysis is based on a treatment policy estimand introduced in [Section 1.2.1](#).

This primary estimand is defined according to the following attributes:

- The endpoint is RR, as defined in [Section 4.3.1](#).
- The treatment condition of interest is isatuximab
- The analysis population is the efficacy-evaluable population (defined in [Section 3](#))
- The study intervention interruption/discontinuation intercurrent event will be handled with the treatment policy strategy. RR will be assessed based on the 3 criteria irrespective of study intervention interruption/discontinuation.
- Population-level summary will be RR, defined as the proportion of participants meeting at least one of the predefined desensitization efficacy criteria (refer to [Section 4.3.1](#)), along with and two-sided 95% confidence intervals using the Clopper-Pearson method.

Proportion of participants meeting each criterion will also be tabulated.

Calculation details and examples on RR criteria 1 and 2 are provided in Appendix 4, [Section 5.4.2](#) (DESENSITIZATION response criteria).

For RR criterion 3, elimination of anti-HLA-antibody will be determined for each applicable molecular specificity.

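### The primary estimand has no rule for non-study desensitization or other prohibited immunosuppression in follow-up, so a response first seen after such therapy counts for isatuximab

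*SAP*

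**What the plan says.** **Estimand.** SAP 1.2.1, Table 2, lists a single intercurrent event, interruption or discontinuation of the study drug: "Response rate will be analyzed regardless of intervention discontinuation (treatment policy". SAP 4.3.2 repeats it: "RR will be assessed based on the 3 criteria irrespective of study intervention interruption/discontinuation". Neither place mentions non-study desensitization, other immunosuppression or transplant.

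**Endpoint and population.** SAP 4.3.1 defines a responder as a participant who meets any one of three criteria "from baseline up to 26 weeks after treatment period, measured by SAB assay per central laboratory assessment". The efficacy-evaluable population (SAP 3) requires eligibility, at least 75% of planned dose, and participants "with an evaluable baseline and at least 1 evaluable postbaseline efficacy assessment". It does not remove anyone for prohibited therapy. The one sensitivity analysis of the response rate (SAP 4.3.3) concerns cohort assignment, and SAP 4.3.4 plans no supplementary analysis.

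**Other therapy.** Protocol 6.5 prohibits "Concurrent treatment with any desensitization procedure or anti-neoplasm therapy not specified in the protocol" and, with listed exceptions, other immunosuppression. The duration is given as "Prohibited concomitant medications (until end of Site Visit FUP, or E/D, or participant undergoes transplantation) are described below". Footnote f of the Schedule of Activities (Protocol 1.3) nevertheless lets hepatitis B monitoring, set for follow-up Weeks 9 and 25, run to those visits "or until initiation of further desensitization therapy/transplant surgery". Footnote m, on the medication row, says "Include any desensitization therapy".

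**Sampling and DoR.** The Schedule of Activities has central cPRA and single antigen bead draws every 4 weeks in site visit follow-up and at E/D, with none in extended follow-up. SAP 4.4.2.1 ends DoR at loss of all criteria or death, and otherwise censors it at the last assessment showing response.

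**The concern.** The endpoint is a best-ever response in an uncontrolled trial. SAP 2 justifies the null response rate by expecting no fall in antibody or cPRA among patients who have no desensitization therapy. A sample drawn after such therapy lies outside that premise. Protocol 2.1.2 itself reports that such therapy can work: IVIG reduced panel reactive antibody against placebo, and IVIG plus rituximab lowered the mean by 44%. The third criterion needs only one antibody to fall from MFI 3000 or more to below 2000.

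A participant who does not respond to isatuximab, starts other therapy and stays in follow-up could therefore be scored a responder. DoR, which Protocol 3.1 includes to address antibody rebound, could likewise be sustained by the other therapy.

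**Working it through.** **1. Can a sample after other therapy decide the endpoint?** Two post-baseline central draws fall in treatment (Cycle 2 Day 1 and Cycle 3 Day 1). If follow-up draws run from Week 1 to Week 25 every 4 weeks (my reading of the schedule), there are (25 − 1)/4 + 1 = 7 in follow-up. Most chances to respond therefore come after treatment. No section stops these draws, or disregards them, once other therapy starts. For participants who remain sampled, later draws can add a responder but cannot remove one.

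**2. The plan's own figure.** SAP 2 states at least 80% power with 12 per cohort, 1-sided alpha 0.025, exact test. Both rates are blacked out, which is not a fault of the plan, so the power cannot be reproduced. The null p0 below is my assumption. The critical count r is the smallest with P(X ≥ r | n = 12, p0) ≤ 0.025, and p1 is the smallest rate giving 80% power.

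| Assumed p0 | r of 12 | Exact alpha | p1 for 80% power |
|---|---|---|---|
| 1% | 2 | 0.0062 | 23.0% |
| 5% | 3 | 0.0196 | 32.4% |
| 10% | 5 | 0.0043 | 49.7% |
| 20% | 6 | 0.0194 | 57.8% |
| 30% | 8 | 0.0095 | 73.1% |

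The planned Clopper-Pearson limits agree: 2/12 has a 95% interval of 2.1% to 48.4%, clear of 1%, and 3/12 has 5.5% to 57.2%, clear of 5%.

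**3. Size per participant.** 1/12 = 8.3 points; 2/12 = 16.7 points. With a low null, where 2 or 3 responders suffice, one or two misattributed responses could decide a cohort.

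**4. Illustration of the error rate.** Let c be the share of non-responders converted by other therapy (assumed; the documents give no figure). The observed rate is p0 + (1 − p0)c. For p0 = 1% and c = 5% it is 0.01 + 0.99 × 0.05 = 0.0595, and P(X ≥ 2) = 0.157. In head count, c = 5% is 12 × 0.99 × 0.05 = 0.59 of a participant per cohort.

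| Assumed p0 (r) | c = 0 | c = 5% | c = 10% |
|---|---|---|---|
| 1% (2) | 0.006 | 0.157 | 0.382 |
| 5% (3) | 0.020 | 0.105 | 0.247 |
| 10% (5) | 0.004 | 0.021 | 0.060 |

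Entries are the chance of a significant result when the true isatuximab response rate equals the null. If responses first met after other therapy are not counted, the values return to the c = 0 column.

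**5. Transplant.** Protocol 4.1 and Schedule of Activities footnote b place the E/D visit before transplant if clinically feasible, followed by extended follow-up, which has no central draw. Protocol 7.1.1, for transplant during treatment, times the E/D visit at 30 ± 7 days after the last dose and does not place it before transplant. Only that difference could produce a central sample after transplant.

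**The case against.** **Three stronger readings are tempting, and the documents support none of them.**

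- A reader might infer that the plan has chosen to credit every later sample to isatuximab. The treatment policy wording covers only isatuximab interruption or discontinuation. On other therapy the SAP is silent, so this is a gap, not a declared choice.
- A reader might infer that samples after transplant are credited as a matter of course. Transplanted participants leave central sampling, so DoR is in effect censored at the pre-transplant visit. What remains is the E/D timing conflict above.
- A reader might infer that these events can only raise the response rate or lengthen DoR. Transplant ends sampling and can lower the rate. For DoR, a lengthening is possible but not certain.

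**The sponsor can also say** that the therapy is banned and that footnote f concerns hepatitis B monitoring in a subgroup and predicts no use. The medication records and date rules also serve extended follow-up, outside the endpoint window. All of that is fair: the documents show the event is contemplated, not that it is likely. Deviations (SAP 4.2) and desensitization medications (SAP 5.3) will be summarised, so its occurrence would be visible. But a listing does not change the response rate or the interval reported.

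**One practical objection stands.** SAP 5.4.1 sets a wholly missing start date for such therapy to treatment end + 1. Used as a cut-off, that would discard every follow-up sample for the participant and leave only the two on-treatment draws.

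**Conclusion.** The concern holds in limited form. For non-study desensitization or other prohibited immunosuppression during site visit follow-up, the estimand states no strategy, and the rules as written count a criterion first met afterwards as an isatuximab response. DoR has the same gap. Among participants still being sampled, the effect on the response rate can only be upward.

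The size is 8.3 points per misattributed responder in a cohort of 12. The effect is conditional: it needs a participant without an earlier response who takes a banned therapy, stays in follow-up and then crosses a threshold. How many will do so is unknown. The error rates shown rest on assumed null rates and assumed conversion shares. They show sensitivity at this sample size and are not a forecast.

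**What to change.** - **Name the event** in SAP Table 2 and 4.3.2: first non-study desensitization or other prohibited immunosuppression, excluding protocol premedication and the corticosteroid use that Protocol 6.5 permits. State also whether immunosuppression given for a life-threatening emergency, which 6.5 allows, belongs to it.
- **Response:** count only participants who meet a criterion on a central sample drawn before that therapy. Keep the others in the denominator as non-responders.
- **DoR (SAP 4.4.2.1):** censor at the last central sample before that therapy.
- **Sensitivity analysis (SAP 4.3.3):** report the response rate using all samples.
- **Missing start dates:** do not use the treatment-end + 1 imputation of SAP 5.4.1 as the cut-off without a stated rule and a check of its effect. One option is to show the response rate under the earliest and the latest possible start date.
- **Transplant:** reconcile the E/D timing in Protocol 7.1.1 with Protocol 4.1 and Schedule of Activities footnote b. State that a central sample drawn after transplant does not count toward response.

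The cost is SAP wording, one date rule and the protocol reconciliation. The therapy is already recorded, so no new data are needed. The downside is a possibly slightly lower response rate.

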2 SAMPLE SIZE DETERMINATION

Statistical hypotheses and sample size determination:

Phase 1: There is no formal statistical hypothesis. Approximately 6 to 12 safety evaluable participants are expected to be enrolled.

Phase 2:

- Null hypothesis: True RR [REDACTED]
- Alternative hypothesis: True RR [REDACTED]

With a minimum sample size of 12 participants per cohort and 1-sided alpha of 0.025, the analysis will have at least 80% power to demonstrate that RR is significantly better than [REDACTED] assuming the true RR is [REDACTED], based on exact test. A null hypothesis of [REDACTED] is selected representing placebo control as there is currently no approved or standard therapy for desensitization, and there is no expected decrease in anti-HLA antibody levels or cPRA in patients who do not undergo desensitization therapy.

A maximum of 6 replacements per cohort is allowed for participants who:

- enroll in Phase 1 and receive <90% of the planned cumulative doses within the first cycle (unless they discontinue IMP due to pre-defined unacceptable toxicity), or
- receive <75% of planned cumulative doses within 3 cycles, or
- have consecutive dose interruption of >28 days, or
- do not complete site visit FUP, after agreement with Medical Monitor.

Participants treated at the Phase 2 dose during Phase 1 will be included in the analysis together with the participants in Phase 2.

3 ANALYSIS POPULATIONS

The following populations for analyses are defined:

Table 3 - Populations for analyses

Population	Description
Screened	All participants who sign the informed consent form (ICF).
Enrolled	Includes all participants from screened population who plan to continue in the treatment phase upon completion of screening, regardless of whether the study intervention (isatuximab) was received or not.
All treated	Includes all participants who receive at least 1 dose of isatuximab-. This population is the primary population for the analyses of safety parameters, unless otherwise noted. All analyses using this population will be based on the dose level actually received.
Safety-evaluable (Phase 1)	Includes all participants enrolled in Phase 1 who receive $\geq 90\%$ planned cumulative doses of isatuximab within Cycle 1 (unless IMP is discontinued due to pre-defined unacceptable toxicity).
Efficacy-evaluable	Includes All Treated population who fulfill the study eligibility criteria, with an evaluable baseline and at least 1 evaluable postbaseline efficacy assessment and receive $\geq 75\%$ of planned cumulative doses. This is the primary population for efficacy analyses.
PK	Includes All Treated population with at least 1 available concentration result post-treatment (whichever the cycle and even if dosing is incomplete) with adequate documentation of date and time of dosing and date and time of sampling.
ADA	Includes All Treated population with at least 1 available ADA result (negative, positive, or inconclusive) post-treatment (whichever the cycle and even if dosing is incomplete).

Participants exposed to isatuximab before or without being enrolled will not be considered enrolled and will not be included in any analysis population. The safety experience of these participants will be reported separately.

Enrolled participants for whom it is unclear whether they took isatuximab will be considered as treated and will be included in the safety population.

